## Combinedb elevation of AST or ALT and concurrent total bilirubinc

For patients with normal baseline ALT or AST or total bilirubin value: AST or ALT >3.0 x ULN combined with total bilirubin >2.0 x ULN without evidence of cholestasis d	Discontinue study treatment permanently in the absence of signs of cholestasis, hemolysis, and if alternative causes of the liver injury have been excluded (e.g., concomitant use of hepatotoxic drug(s), alcoholic hepatitis, viral hepatitis etc.)
OR	
	Repeat LFTs as soon as possible, preferably
For patients with elevated baseline AST or	within 48 hours from awareness of the abnormal
ALT or total bilirubin value:	results, then with weekly monitoring of LFTs b ),
[AST or ALT>2x baseline AND > $3.0xULN$ ]	or more frequently if clinically indicated, until
OR [AST or ALT $> 8.0 \times ULN$ ], whichever is	AST, ALT, or bilirubin have resolved to baseline
lower, combined with [total bilirubin >2x	or stabilized over 4 weeks. Testing for viral
baseline AND >2.0xULN]	hepatitis infection or reactivation should be
	performed, see Section 6.1.3 and Table 6-5.

a. If Grade 3 or 4 hyper-bilirubinemia is due to the indirect (non-conjugated) component only, and hemolysis as the etiology has been ruled out as per institutional guidelines (e.g., Review of peripheral blood smear and haptoglobin determination), then  $\downarrow 1$  dose level and continue treatment at the discretion of the investigator.

*b.* "Combined" defined as: total bilirubin increase to the defined threshold concurrently with ALT/AST increase to the defined threshold

c. If combined elevations of AST or ALT and total bilirubin do not meet the defined thresholds, please follow the instructions for isolated elevation of total bilirubin and isolated elevation of AST/ALT, and take a conservative action based on the degree of the elevations (e.g. discontinue treatment at the situation when omit dose is needed for one parameter and discontinue treatment is required for another parameter). After all elevations resolve to the defined thresholds that allow treatment re-initiation, re-start the treatment either at the same dose or at one dose lower if meeting a criterion for dose reduction

*d.* "Cholestasis" defined as: ALP elevation (>2xULN and R value< 2) in patients without bone metastasis, or elevation of ALP liver fraction in patients with bone metastasis

*Note: The R value is calculated by dividing the ALT by the ALP, using multiples of the ULN for both values. It denotes the relative pattern of ALT and/or ALP elevation is due to cholestatic or hepatocellular liver injury* 

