# 6.1.2 Management of liver function abnormalities (bilirubin, AST, ALT)

# Table 6-4: Guidelines for management of abnormal LFTs: Investigations (Henatic)a

Investigations (Hepatic) a		
Total Bilirubin (for patients with Gilbert Syndrome these dose modifications apply to changes in		
direct [conjugated] bilirubin only)		
Grade 1 (>ULN and $\leq 1.5 \times ULN$ )	Maintain dose level with liver function test	
	(LFTs) monitored as per protocol	
Grade 2 (>1.5 and $\leq$ 3.0 x ULN) with ALT or	Omit both drugs until resolved to $\leq$ grade 1, then:	
$AST \leq 3.0 x ULN$	If resolved in $\leq$ 7 days, then resume EGF816 at	
	the original dose level with close LFT	
	monitoring. Resume gefitinib at the original dose	
	level if LFTs remain < g rade 1 after 7 days of	
	EGF816.	
	If resolved in $>7$ days, then resume drugs one at a	

	time (as above) with one level dose reduction in each drug.
Grade 3 (>3.0 and ≤10.0 x ULN) with ALT or AST ≤3.0 x ULN	Omit both drugs until resolved to $\leq$ grade 1, then: If resolved in $\leq$ 7 days, resume EGF816 with one level dose reduction and close LFT monitoring. Resume gefitinib with one level dose reduction if LFTs remain $\leq$ grade 1 after 7 days of EGF816. If resolved in $\Box$ 7 days discontinue patient from study treatment.
	The patient should be monitored weekly (including LFTs b ), or more frequently if clinically indicated, until total bilirubin has resolved to baseline or stabilized over 4 weeks.
Grade 4 (>10.0 x ULN)	Permanently discontinue study treatment. The patient should be monitored weekly (including LFTs), or more frequently if clinically indicated, until total bilirubin has resolved to baseline or stabilized over 4 weeks.
AST or ALT	
Grade 1 (>ULN and $\leq 3.0 \text{ x ULN}$ )	Maintain dose level with LFTs monitored per protocol
Grade 2 (>3.0 and ≤5.0 x ULN) without total bilirubin elevation to >2.0 x ULN	Maintain dose level with LFTs monitored per protocol
Grade 3 (>5.0 and ≤20.0 x ULN) without total bilirubin elevation to >2.0 x ULN	Omit both drugs until resolved to $\leq$ Grade 1 (or to baseline), then resume EGF816 with one level dose reduction and close LFT monitoring. Resume gefitinib with one level dose reduction if LFTs remain $\leq$ grade 1 after 7 days of EGF816. Permanently discontinue study treatment if $\geq$ Grade 3 elevation recurs.

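### Table 6-4's combined AST/ALT and bilirubin row gives no dosing instruction during work-up, so one serious liver pattern has no required hold while a milder one does

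*Combined protocol and SAP*

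**What the plan says.** Table 6-4 (Section 6.1.2) handles isolated bilirubin elevation, isolated AST/ALT elevation and the combination in separate rows.

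- **Combined row.** For a normal baseline, the trigger is AST or ALT above 3 x ULN with bilirubin above 2 x ULN and no cholestasis. The dosing action is "Discontinue study treatment permanently in the absence of signs of cholestasis, hemolysis, and if alternative causes of the liver injury have been excluded". The remaining instructions are repeat liver tests, preferably "within 48 hours from awareness of the abnormal" results, then weekly monitoring and viral hepatitis testing.
- **Bilirubin Grade 2 row.** The trigger begins "Grade 2 (>1.5 and $\leq$ 3.0 x ULN) with ALT or" and ends with AST at or below 3 x ULN. The action begins "Omit both drugs until resolved to" Grade 1 or better. The Grade 3 row has the same enzyme qualifier and also starts with a hold.
- **Bilirubin Grade 4 row.** "Grade 4 (>10.0 x ULN") means permanent discontinuation, with no enzyme qualifier.
- **AST/ALT Grade 2 row.** "Grade 2 (>3.0 and ≤5.0 x ULN) without total bilirubin elevation to >2.0 x ULN": dose maintained. The Grade 3 and 4 rows hold both drugs but carry the same bilirubin exclusion.
- **Footnote c.** "If combined elevations of AST or ALT and total bilirubin do not meet the defined thresholds, please follow the instructions for isolated elevation", and "take a conservative action based on the degree of the elevations".

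Table 6-3 (Section 6.1) gives general rules for toxicities at least possibly drug-related: maintain at Grades 1 and 2, omit both drugs at Grade 3, stop permanently at Grade 4. It refers the reader to the later subsections for specific toxicities, including liver abnormalities.

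**The concern.** The protocol itself treats the combined pattern as serious, since its end point is permanent discontinuation. Yet that action depends on excluding other causes, which takes time, and the row does not say what happens to dosing meanwhile. The default in Section 5.1 is continuous daily dosing unless an interruption is needed for treatment-related toxicity.

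A site following the tables could therefore keep a patient with possible drug-induced liver injury on two daily EGFR inhibitors during the work-up. Section 2.3 lists hepatotoxicity among gefitinib's rare but serious effects. Section 2.2.2 records one death from hepatitis B reactivation judged related to EGF816, and viral hepatitis is among the causes this work-up must exclude. Elsewhere the protocol writes the hold out: Grade 2 pneumonitis (Section 6.1.1) and HBV reactivation (Table 6-6) both interrupt both drugs.

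**Working it through.** No sample size, power or error rate is involved, so there is no planned figure to reproduce. The check is whether any rule requires a hold.

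**Two patients side by side.** Both have normal baseline, no cholestasis and no existing hold. Values are multiples of ULN.

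| Rule | A: AST 4, ALT 4, bilirubin 2.5 | B: AST 2, ALT 2, bilirubin 2.5 |
|---|---|---|
| Bilirubin Grade 2 row | Closed: neither enzyme is at or below 3 | Open: omit both drugs |
| AST/ALT Grade 2 row | Closed: bilirubin exceeds 2 | Not reached |
| Combined row | Open: stop only after exclusions; no interim action | Not reached |
| Footnote a | Not applicable: Grade 3-4 bilirubin only | Not applicable |
| Footnote c | Not applicable: thresholds are met | Not needed |
| Table 6-3 default | Grade 2: maintain | Not needed |

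B is held immediately. A has the same bilirubin and higher enzymes, and has no stated hold.

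**Other provisions for A.**
- Section 6.1 lets the treating investigator modify the guidelines. This permits a hold.
- Section 5.2.2 allows a delay for toxicities that already require one. No row says this pattern does.
- Section 6.1.3 interrupts both drugs once a new viral infection is found, not while results are pending.
- Section 6 bases dose changes on the worst preceding toxicity. I read this as keeping an already-held patient on hold, so such patients are outside the gap.

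**How wide the gap is.** Set AST and ALT each at 2, 4, 6 and 25 x ULN and bilirubin at 1, 1.8, 2.5, 4 and 12 x ULN: 4 x 4 x 5 = 80 cells.

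- Combined trigger (higher enzyme above 3, bilirubin above 2): 16 - 1 = 15 enzyme pairs x 3 bilirubin bands = 45 cells.
- Bilirubin at 12 is already permanent discontinuation: 15 cells covered, 30 left.
- Literal reading (one enzyme at or below 3 keeps the bilirubin hold open): 3 x 3 = 9 pairs with both enzymes above 3, x 2 bilirubin bands = 18 cells with no Table 6-4 hold.
- Strict reading (both enzymes must be at or below 3): 15 x 2 = 30 cells with no Table 6-4 hold.

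Applying Table 6-3 at the worst grade:

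| Reading | No Table 6-4 hold | Table 6-3 stops | Table 6-3 omits | Table 6-3 maintains |
|---|---|---|---|---|
| Literal | 18 | 10 | 7 | 1 |
| Strict | 30 | 14 | 13 | 3 |

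The one literal cell is (AST 4, ALT 4, bilirubin 2.5). The strict reading adds (4, 2, 2.5) and (2, 4, 2.5). The zone with no hold from either table is therefore 1 to 3 of 80 cells. These are chosen bands, not patient frequencies.

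**Exposure if nobody acts.** One dose of each drug per day x 2 days = about 2 doses of each by a 48-hour repeat, then 7 of each per further week.

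**The case against.** The strongest reply is that holding is already allowed and would be no deviation. The table is headed as guidelines, Section 6.1 gives the investigator discretion, and Section 5.1 permits interruption for treatment-related toxicity. Many investigators would hold a patient whose laboratory pattern is marked for permanent discontinuation. Part of the work-up is also quick, since ALP is on the routine chemistry panel. All of this stands, and it makes the exposure count an upper case. It does not supply an instruction.

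Three stronger readings are tempting and should not be adopted.

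- **That the protocol directs continued dosing.** It does not. Table 6-3 defers to Section 6.1.2 for liver abnormalities, so its Grade 2 rule is only a default where that section is silent. The accurate statement is that the interim action is unstated.
- **That every combined elevation is unprotected.** With Table 6-3 as fallback, a Grade 3 or higher value brings a hold or stop. With an elevated baseline, the same levels may miss the combined thresholds, and footnote c then supports a conservative action.
- **That AST/ALT 4 with bilirubin 1.8 x ULN is held while 4 with 2.5 is not.** At 1.8 the bilirubin Grade 2 hold is closed by its own enzyme qualifier, and the AST/ALT Grade 2 row maintains dosing. A hold follows only if footnote c is read as setting that qualifier aside. The firm comparator is the patient with AST and ALT at or below 3 x ULN.

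**Conclusion.** The gap is real and narrow. For a normal-baseline patient not already on hold, without cholestasis, with AST and ALT both above 3 and up to 5 x ULN and bilirubin above 2 and up to 3 x ULN, nothing requires a hold while other causes are excluded. A milder pattern with the same bilirubin is held at once. Confidence is high in the textual omission and lower in its practical consequence.

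The documents give no rate for the pattern. Section 2.2.2 lists no AST, ALT or bilirubin event among any-grade events in more than 10% of the 148 patients on EGF816 alone, so it is probably uncommon; no rate is given for the combination. The conclusion assumes Table 6-3 is the general fallback. This is a cheap patient-safety improvement and does not affect the trial's statistical design.

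**What to change.** Add to the combined row of Table 6-4: *Omit both EGF816 and gefitinib as soon as the combined thresholds are met, pending work-up; discontinue permanently if cholestasis, hemolysis and alternative causes are excluded.*

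The change should stop there. A restart rule tied to the bilirubin rows would be unsafe: the Grade 2 row reduces both drugs when resolution takes more than 7 days, and the Grade 3 row appears to discontinue after slower recovery (its symbol is garbled in the text). A patient whose injury proved unrelated to drug could lose dose or treatment. A change to footnote a is not needed either, since it concerns Grade 3-4 bilirubin and the gap lies at Grade 2.

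The cost is one sentence at the next amendment, with no extra patients or tests. The downside is a short dose interruption in a few patients whose elevation proves unrelated to drug.

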#### 6.1.3 Guidelines for screening, monitoring and management of HBV/HCV reactivation

HBV screening tests, on study monitoring, and management of HBV reactivation:

1. All patients must be screened with HBV serologic markers: HBsAg, HBsAb, and HBcAb.

- 2. If HBsAg and/or HBcAb are positive, test for HBV-DNA.
- 3. Refer to Table 6-5 for actions to be taken based on screening HBV results.
- 4. If a patient is HBsAg positive or HBV-DNA positive BUT is not on antiviral therapy:
  - a. Consult a physician with expertise in managing HBV
  - b. Initiate antiviral therapy with entecavir 0.5mg QD 1-2 weeks prior to first dose of EGF816 treatment.
  - c. If a patient cannot take entecavir, contact the principal investigator to select an appropriate antiviral therapy.
  - d. If antiviral therapy cannot be given, the patient is not eligible for the study.
  - e. During the study, monitor HBV-DNA every 12 weeks (or more frequently if clinically indicated). (Refer to Table 6-6 if there is evidence of viral reactivation on study)
  - f. Antiviral therapy should continue for at least 4 weeks after the last dose of EGF816.
- 5. Patients who are HBsAg positive or HBV-DNA positive at screening and already have been receiving antiviral therapy are eligible provided the patient remains on antiviral treatment.
  - a. Identify a consulting physician with expertise in managing HBV who can provide treatment guidance, if required, while the patient is on study.
  - b. HBV-DNA should be monitored every 12 weeks (or more frequently if clinically indicated).
  - c. Antiviral therapy should continue for at least 4 weeks after the last dose of EGF816.
- 6. Refer to Table 6-6 for guidelines of management for HBV reactivation.

Test	Result	Result	Result	Result	Result
HBV-DNA	+	+ or -	-	-	-
HBsAg	+ or -	+	-	-	-
HBsAb	+ or -	+ or -	+ and no prior HBV vaccination	- or + with prior HBV vaccination	- or + with prior HBV vaccination
HBcAb	+ or -	+ or -	+ or -	+	-

Table 6-5: Actions to be taken based on hepatitis B results screening

NCI Protocol #: DF/HCC Protocol #: 17-291 Protocol Version Date: January 10th, 2019

Test	Result	Result	Result	Result	Result
Required actions	* Consult a physician with expertise in managing HBV. After the consultation, antiviral therapy should be started 1-2 weeks			ral therapy. IBV-DNA eeks.	No antiviral therapy.
	
 
prior to 1st dose of EGF816 treatment.
 
Recommended antiviral therapy is entecavir 0.5mg QD. Contact the study PI if a patient cannot take entecavir.
 
Monitor HBV-DNA every 12 weeks (or more frequently if clinically indicated).
 
Antiviral therapy should continue for at least 4 weeks after the last dose of EGF816.
 
				HBV-DNA screening not required unless HBsAg and/or HBcAb are positive

Table 6-6 Guidelines for management of HBV reactivation

HBV reactivation (with or without clinical signs and symptoms)*			
Screening test results	Monitoring test results that define HBV reactivation	Actions to be taken	
Positive HBV- DNA OR	Increase of 1 log in HBV-DNA relative to screening HBV- DNA value	Interrupt EGF816 and gefitinib treatment. Assess patient compliance with antiviral therapy. Consult a physician with expertise in managing HBV and consider changing antiviral therapy.	
Positive HBsAg	OR New appearance of measurable HBV- DNA	
 
While patient is on antiviral therapy, continue interruption of EGF816 administration until resolution to:
 
≤ screening HBV-DNA levels and
 
≤ grade 1 ALT (or baseline ALT, if > grade 1) if ALT elevation was observed
 
	
		
 
If resolution occurs within ≤ 21 days EGF816 and gefitinib should be re-started, one at a time, at the same dose level unless dose reduction/interruption is indicated due to any other reason. Resume EGF816 first with close LFT monitoring. Resume gefitinib if LFTs remain ≤ grade 1 after at least 7 days of EGF816. Antiviral therapy should continue for at least 4 weeks after the last dose of EGF816.
 
If resolution occurs > 21 days, contact study PI for approval of restarting of EGF816 and gefitinib is approved: follow the same guidelines as above.
 
If restarting of EGF816 and gefitinib is NOT approved: discontinue study treatment. Continue antiviral therapy for at least 4 weeks after the last dose of EGF816
 
Monitor HBV-DNA every 12 weeks (or more frequently if clinically indicated).
 
	

Screening test results	Monitoring test results that define HBV reactivation	ical signs and symptoms)* Actions to be taken
Negative HBV- DNA	New appearance of measurable HBV- DNA	Interrupt EGF816 and gefitinib treatment. Consult a physician with expertise in managing HBV. After the consultation, start antiviral therapy.
AND		While patient is on antiviral therapy, continue interruption of EGF816 and gefitinib
Negative HBsAg		administration until resolution to:
		
 
≤ baseline HBV-DNA levels and
 
≤ grade 1 ALT (or baseline ALT, if > grade 1) if ALT elevation was observed If resolution occurs within ≤ 21 days EGF816 and gefitinib should be re-started at the same dose level unless dose reduction/interruption is indicated due to any other reason. Reintroduce EGF816 first; if LFT remains ≤ grade 1 after at least 7 days on EGF816, resume gefitinib. Antiviral therapy should continue for at least 4 weeks after the last dose of EGF816. If resolution occurs > 21 days Contact study PI for approval of restarting of EGF816.
 

		If restarting of EGF816 and gefitinib is approved: follow the same guidelines as above.
		If restarting of EGF816 and gefitinib is NOT approved: discontinue EGF816 treatment. Continue antiviral therapy for at least 4 weeks after the last dose of EGF816.
* All pageting of	HRV are to be recorded as	Monitor HBV-DNA every 12 weeks (or more frequently if clinically indicated).

\* All reactivations of HBV are to be recorded as serious adverse event (SAE). Date of viral reactivation is the date on which the defined lab results for reactivation were met (e.g. for a patient who was HBV-DNA positive on 01-JAN-15 and whose ALT reached > 5 × ULN on 01-APR-15, the date of viral reactivation is 01-APR-15).

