- 3.1.7 Patients must be screened for HBV. Patients who are either HBsAg positive or HBV-DNA positive must be willing and able to take antiviral therapy 1-2 weeks prior to 1st dose of study treatment and continue on antiviral therapy for at least 4 weeks after the last dose of EGF816. Additional management of the patients would be provided by a physician with expertise in management of HBV, if needed. Patients must have negative hepatitis C antibody (HCV-Ab) or positive HCV-Ab but undetectable level of HCV-RNA. Note: patients with detectable HCV-RNA are not eligible for the study.
- 3.1.8 Patients must receive insurance approval for or be willing to pay for commercial gefitinib.
- 3.1.9 Age  $\geq$  18 years.
- 3.1.10 ECOG performance status  $\leq 2$  (Karnofsky  $\geq 60\%$ , see Appendix A)
- 3.1.11 Life expectancy of greater than 12 weeks.
- 3.1.12 Participants must have normal organ and marrow function as defined below:
  - Leukocytes  $\geq$ 3,000/mcL
  - Absolute neutrophil count  $\geq$ 1,500/mcL
  - Platelets  $\geq 100,000$ /mcL
  - Total bilirubin <1.5 x upper limit of normal (ULN) \**For patients with Gilbert's syndrome total bilirubin* <3.0 x ULN
    - AST(SGOT)/ALT(SGPT) ≤3 × institutional upper limit of normal; for patients with known hepatic metastases AST and/or ALT > 5x ULN
    - Creatinine  $\leq 1.5 \times$  institutional upper limit of normal
- 3.1.13 The effects of EGF816 and gefitinib on the developing human fetus are unknown. For this reason, women of child-bearing potential and men must agree to use highly effective contraception during the study and for 3 months after stopping the study treatment. Highly effective contraception methods include:
  - Total abstinence (when this is in line with the preferred and usual lifestyle of the subject. Periodic abstinence (e.g., calendar, ovulation, symptomthermal, postovulation methods) and withdrawal are not acceptable methods of contraception
  - Female sterilization (have had surgical bilateral oophorectomy with or without hysterectomy) or tubal ligation at least six weeks before taking study treatment. In case of oophorectomy alone, only when the reproductive status of the woman has been confirmed by follow up hormone level assessment

- Male Partner: male sterilization (at least 6 months prior to screening). For female subjects on the study the vasectomized male partner should be the sole partner for that subject.
- **Combination** of any **two** of the following (a+b or a+c, or b+c):

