#### Table 10-1 Study Calendar

\* Re-consent is required if treatment starts more than 28 days after the original consent.

- a. Treatment with EGF816 and gefitinib can be continued beyond progression at the discretion of the treating investigator (see section 5.5)
- b. Sodium, potassium, calcium, magnesium, glucose, creatinine, total bilirubin, alkaline phosphatase [ALP], aspartate transaminase [AST], alanine transaminase [ALT], blood urea nitrogen [BUN], total protein, albumin and lactic dehydrogenase [LDH]. If screening chemistry is drawn > 7 days before C1D1, chemistry should be redrawn on C1D1. These do not need to re-meet eligibility.
- c. Screening labs should include HBsAg, HBsAb, HCV-Ab, and HBcAb. Check HBV-DNA if HBsAg and/or HBcAb are positive (see section 6.1.3). In addition, HBV DNA and/or HCV RNA monitoring will be required for some patients based on initial screening (see section 6.1.3)
- d. Urinalysis should be performed at baseline and then only if clinically indicated.
- e. Radiologic evaluation (CT chest, abdomen and pelvis) should be performed every 8 weeks of treatment. After completing 1 year of treatment, radiologic evaluations should be performed every 12 weeks. Brain imaging (MRI, or CT with contrast in patients with contraindications to MRI) should be obtained every 8 weeks for patients with known brain metastases at the start of treatment. For patients without known baseline brain metastases, CNS imaging should be obtained if clinically indicated based on symptoms.
- f. Pre-treatment core needle or excisional should be done within 28 days of start of treatment
- g. On-treatment biopsy should be performed between D15 and D21 of cycle 1. On the day of the on-treatment biopsy, patients should take both study drugs. Their morning gefitinib dose can be taken with sips of water.
- h. Post-treatment core needle biopsy should be obtained at the time of disease progression. The exact timing of this biopsy will be at the discretion of the treating investigator, but must occur at or after the patient reaches PD by RECIST.
- i. Cycle 1, Day 3 ctDNA blood draw should be performed as close to 48 hours after first dose as possible.
- j. Pre-dose steady state levels of EGF816 and gefitinib will obtained on C1D1 and C1D15.

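### No screening HBV-DNA test is ordered for one serology pattern (HBsAg-negative, HBcAb-negative, HBsAb-positive, unvaccinated) that Table 6-5 classifies by HBV-DNA

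*Combined protocol and SAP*

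**What the plan says.** Section 6.1.3, step 1, sets the universal panel: "All patients must be screened with HBV serologic markers: HBsAg, HBsAb, and HBcAb". HBV-DNA is not part of it. Step 2 gives the trigger for that test: "If HBsAg and/or HBcAb are positive, test for HBV-DNA". Note c of the study calendar (Table 10-1) states the same trigger. A positive HBsAb does not prompt the test in either place.

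Step 3 sends the site to Table 6-5, which has five result columns. Three matter here:

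- **Column 1:** HBV-DNA positive, any serology. Antiviral therapy starts before the first dose.
- **Column 3:** HBV-DNA negative, HBsAg negative, HBsAb positive "and no prior HBV vaccination", HBcAb either positive or negative.
- **Column 5 (the last):** HBV-DNA negative, HBsAg negative, HBcAb negative, and HBsAb either negative or positive after vaccination. Its action cell carries the waiver "HBV-DNA screening not required unless HBsAg and/or HBcAb are positive".

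Criterion 3.1.7 uses the result for eligibility: "Patients who are either HBsAg positive or HBV-DNA positive must be willing and able to take antiviral therapy". Step 4d adds: "If antiviral therapy cannot be given, the patient is not eligible for the study".

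Table 6-6 is entered by the screening HBV-DNA and HBsAg results. For patients negative on both, reactivation is "New appearance of measurable HBV- DNA", and resolution includes a return to the baseline HBV-DNA level or below.

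**The concern.** The rule that orders the test and the table that uses its result do not cover the same patients. A patient who is HBsAg-negative, HBcAb-negative and HBsAb-positive without vaccination belongs in column 3 if HBV-DNA is negative and in column 1 if it is positive. A site that follows step 2 has no HBV-DNA result with which to choose.

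Two things are at stake. An HBV-DNA-positive patient of this type could start treatment without meeting the antiviral condition of 3.1.7. And if HBV-DNA is first found during the study, nobody can say whether it is new or was there at entry. That distinction matters because a reactivation under Table 6-6 interrupts both drugs and is recorded as a serious adverse event, which section 7.2.3 requires to be reported to Novartis within 24 hours.

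**Working it through.** The plan gives no figure to reproduce, so the check is a count of serology patterns against the two rules.

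**Inputs.** HBsAg has two states. HBsAb has three (negative, positive after vaccination, positive without vaccination), because Table 6-5 makes that split. HBcAb has two. Patterns: 2 × 3 × 2 = 12.

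**Which are tested.** Step 2 orders HBV-DNA if HBsAg or HBcAb is positive.

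- HBsAg positive: 1 × 3 × 2 = 6 patterns, all tested.
- HBsAg negative, HBcAb positive: 1 × 3 × 1 = 3 patterns, all tested.
- Tested: 6 + 3 = 9. Not tested: 12 − 9 = 3, all HBsAg-negative and HBcAb-negative.

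**Where the three untested patterns fall in Table 6-5.**

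| HBsAb state | Column if HBV-DNA negative | Column if HBV-DNA positive | Waiver printed in the HBV-DNA-negative column? |
|---|---|---|---|
| Negative | 5 | 1 | Yes |
| Positive, vaccinated | 5 | 1 | Yes |
| Positive, unvaccinated | 3 | 1 | No |

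Only the last row is both untested and outside the column that carries the waiver.

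**Following that pattern through the other rules.**

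- *Criterion 3.1.7 and step 4d.* The HBsAg part is known (negative). The HBV-DNA part is not.
- *Table 6-6, entry.* The second row needs a negative screening HBV-DNA as well as a negative HBsAg. An untested patient meets only the HBsAg half.
- *Table 6-6, reactivation.* A new appearance needs a known earlier negative, and the 1-log rise in the first row needs a screening value. Neither exists.
- *Table 6-6, resolution.* A return to the baseline HBV-DNA level has no baseline to refer to.

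**Vaccination history.** Columns 3, 4 and 5 turn on it. Section 5.2 asks for a complete medical history, but neither that section nor note c names HBV vaccination as an item to record.

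**The case against.** The strongest reply is that the testing rule is consistent. Step 2, note c and the waiver all tie the test to HBsAg or HBcAb, and the waiver is worded generally. Column 5 also shows a negative HBV-DNA for patients whom the waiver leaves untested, so a negative entry in this table can mean not tested. On that reading only the label of column 3 is unclear. This is a fair reading of column 5. The documents do not extend it to column 3, though, and if they did, Table 6-6 would still lack a reference value for these patients.

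Safeguards exist: AST and ALT limits at entry; chemistry at screening, C1D8, C1D15 and each cycle; and for every patient an immediate hepatitis panel once ALT crosses the threshold in 6.1.3. They reduce the risk of a missed hepatitis. They do not supply a screening HBV-DNA value.

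A reader might infer four stronger things, none of which the documents support:

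- *That the six-patient run-in trigger could be tripped falsely.* The trigger counts Grade 3 or higher related events in cycle 1, which is 28 days. Legible HBV-DNA monitoring is every 12 weeks, or 12 × 7 = 84 days. An event recorded as serious is also not necessarily Grade 3.
- *That the single-agent data give the risk in this group.* Section 2.2.2 reports one related HBV-reactivation death in 148 patients (1/148 = 0.7%) and related Grade 3/4 HBV events in 1.4% (0.014 × 148 ≈ 2 patients), without baseline serology. This shows that HBV reactivation matters for EGF816, not how often it would arise in this pattern.
- *That 3.1.7 cannot be judged at all.* Only its HBV-DNA part is open.
- *That column 3 expressly requires HBV-DNA monitoring.* In the text available the action cell for columns 3 and 4 is broken. Periodic monitoring is a plausible inference from its remnants, and no more than that.

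**Conclusion.** The mismatch stands for one serology pattern of the 12. It rests on the legible HBV-DNA, HBsAb and HBcAb rows of Table 6-5 and does not depend on the damaged action cell. The position of the waiver in the last column is taken from the table as it appears in the available text. If it was meant to cover column 3 as well, that column's negative HBV-DNA entry would be unverified for HBcAb-negative patients, and the passages would still need aligning.

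The size is modest. The group is probably small, the protocol gives no frequency from which to count it, and HBV-DNA-positive patients would be a subset of it. The primary endpoint calculation is not touched. The point deserves correction because a stated rule can leave an eligibility condition unchecked and a safety event unclassifiable, and the remedy is simple.

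**What to change.** Reconcile section 6.1.3 step 2, note c of Table 10-1 and Table 6-5, and state which columns the waiver covers. After the change, the serology patterns that trigger a screening HBV-DNA test should be the same as those that Table 6-5 sorts by HBV-DNA and Table 6-6 judges against a screening value. Name HBV vaccination history as an item to record at screening. Which of the conflicting passages stands is for the sponsor and its HBV expert to decide.

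The cost is aligned wording in three places and one history item. Whether any patient needs an additional assay depends on that decision. If so, it is one test per affected patient at screening, when blood is already drawn.
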